10.4. Appendix 4: Contraceptive and Barrier Guidance

10.4.1. Definitions

Person of Childbearing Potential

Persons AFAB are considered POCBP (fertile) following menarche:

- From the time of menarche until becoming postmenopausal unless permanently sterile.
- A postmenopausal state is defined as no menses for 12 months without an alternative medical cause.
 - A high FSH level in the postmenopausal range may be used to confirm a postmenopausal state in women not using hormonal contraception or hormonal replacement therapy. However, in the absence of 12 months of amenorrhea, confirmation with more than one FSH measurement is required.
 - Persons AFAB on HRT and whose menopausal status is in doubt will be required to use one of the nonestrogen hormonal highly effective contraception methods if they wish to continue their HRT during the study. Otherwise, they must discontinue HRT to allow confirmation of postmenopausal status before study enrollment.
- Permanent sterilization methods (for the purpose of this study) include:
 - Documented hysterectomy.
 - Documented bilateral salpingectomy.
 - Documented bilateral oophorectomy.
 - For individuals with permanent infertility due to an alternate medical cause other than the above, (eg, Mullerian agenesis, androgen insensitivity, gonadal dysgenesis), Investigator discretion should be applied to determining study entry.

Note: Documentation can come from the site personnel's review of the participant's medical records, medical examination, or medical history interview.

If fertility is unclear (eg, amenorrhea in adolescents or athletes) and a menstrual cycle cannot be confirmed before first dose of study intervention, additional evaluation should be considered.

Person of Nonchildbearing Potential

Persons AFAB in the following categories are considered PONCBP:

1. Premenopausal persons AFAB with permanent infertility due to one of the following:
 - a. Documented hysterectomy.
 - b. Documented bilateral salpingectomy.
 - c. Documented bilateral oophorectomy.
 - d. For individuals with permanent infertility due to an alternate medical cause other than the above, (eg, Mullerian agenesis, androgen insensitivity, gonadal dysgenesis), Investigator discretion should be applied to determining study entry.

Note: Documentation can come from the site personnel’s review of the participant’s medical records, medical examination, or medical history interview.

2. Postmenopausal persons AFAB:

- a. A postmenopausal state is defined as no menses for 12 months without an alternative medical cause.
 - i. A high FSH level in the postmenopausal range may be used to confirm a postmenopausal state in women not using hormonal contraception or hormonal replacement therapy. However, in the absence of 12 months of amenorrhea, confirmation with more than one FSH measurement (>40 IU/L or mIU/mL) is required.
 - ii. Persons AFAB on HRT and whose menopausal status is in doubt must discontinue HRT to allow confirmation of postmenopausal status before study enrollment.

10.4.2. Contraception Guidance

CONTRACEPTIVES^a ALLOWED DURING THE STUDY INCLUDE:
Highly Effective Methods^b That Have Low User Dependency Failure rate of <1% per year when used consistently and correctly.

 • Implantable progestogen-only hormone contraception associated with inhibition of ovulation.

 • IUD.

 • IUS.

 • Bilateral tubal occlusion.

 • Azoospermic partner (vasectomized or due to a medical cause). • Azoospermia is a highly effective contraceptive method provided that the partner is the sole sexual partner of the POCBP and the absence of sperm has been confirmed. If not, an additional highly effective method of contraception should be used. Spermatogenesis cycle is approximately 90 days. 
Note: documentation of azoospermia for a participant can come from the site personnel’s review of the participant’s medical records, medical examination, or medical history interview.

Highly Effective Methods^b That Are User Dependent Failure rate of <1% per year when used consistently and correctly.

Combined (estrogen- and progestogen-containing) hormonal contraception associated with inhibition of ovulation:
 
 Oral. Intravaginal. Transdermal. Injectable.

Progestogen-only hormone contraception associated with inhibition of ovulation:
 
 Oral. Injectable.

CONTRACEPTIVES^a ALLOWED DURING THE STUDY INCLUDE:
Highly Effective Methods^b That Have Low User Dependency Failure rate of <1% per year when used consistently and correctly.
Sexual abstinence. Sexual abstinence is considered a highly effective method only if defined as refraining from heterosexual intercourse during the entire period of risk associated with the study intervention. The reliability of sexual abstinence needs to be evaluated in relation to the duration of the study and the preferred and usual lifestyle of the participant.
Effective Methods That Are Not Considered Highly Effective Failure rate of $\geq 1\%$ per year when used consistently and correctly.

 • Progestogen-only oral hormonal contraception where inhibition of ovulation is not the primary mode of action.

 • External or internal condom with or without spermicide.

 • Cervical cap, diaphragm, or sponge with spermicide.

 • A combination of external condom with either cervical cap, diaphragm, or sponge with spermicide (double-barrier methods)^c.

a. Contraceptive use should be consistent with local regulations regarding the use of contraceptive methods for those participating in clinical studies.
 
b. Failure rate of <1% per year when used consistently and correctly. Typical use failure rates differ from those when used consistently and correctly.
 
c. Considered effective, but not highly effective - failure rate of $\geq 1\%$ per year.
 
Note: Periodic abstinence (calendar, symptothermal, postovulation methods), withdrawal (coitus interruptus), spermicides only, and LAM are not acceptable methods of contraception. External condom and internal condom should not be used together (due to risk of failure from friction).

Abbreviations: IUD=intrauterine device; IUS=intrauterine hormone-releasing system; LAM=lactational amenorrhea method; POCBP=person of childbearing potential.

10.5. Appendix 5: Adverse Event of Special Interest

Investigators should report all events that fall into the categories presented in [Table 8](#) as an AESI per the reporting processes in [Section 10.3.6](#). The following AESIs are medical concepts that are generally of interest in vaccine safety surveillance as per the Brighton Collaboration and Safety Platform for Emergency Vaccines or the vaccine platform.

Table 8: Adverse Events of Special Interest

Medical Concept	Additional Notes
Thrombocytopenia	
 • Platelet counts $<125 \times 10^9$. • Including but not limited to immune thrombocytopenia, platelet production decreased, thrombocytopenia, thrombocytopenic purpura, thrombotic thrombocytopenic purpura, or HELLP syndrome.
New onset of or worsening of the following neurologic diseases:	
 • Guillain-Barre Syndrome. • ADEM. • Idiopathic peripheral facial nerve palsy (Bell’s palsy). • Seizures including but not limited to febrile seizures and/or generalized seizures/convulsions.
Anaphylaxis	
 • Anaphylaxis associated with IP administration as defined per protocol in Section 8.4.8.1. • Follow reporting procedures in Section 10.3.6.
Myocarditis/Pericarditis	
 • Myocarditis. • Pericarditis. • Myopericarditis.

Abbreviations: ADEM=acute disseminated encephalomyelitis; HELLP=hemolysis, elevated liver enzymes and low platelets; IP=investigational product.

10.6. Appendix 6: CDC Working Case Definitions of Pericarditis, Myocarditis, and Myopericarditis Occurring After Receipt of COVID-19 mRNA Vaccines

The CDC Working Case Definitions of probable and confirmed myocarditis, pericarditis, and myopericarditis ([Gargano et al 2021](#)) are provided in [Table 9](#) as guidance.

Table 9: Case Definitions of Probably and Confirmed Myocarditis, Pericarditis, and Myopericarditis

Condition	Definition	
Acute myocarditis	Probable case	Confirmed case
	Presence of ≥ 1 new or worsening of the following clinical symptoms:* 
 • Chest pain, pressure, or discomfort. • Dyspnea, shortness of breath, or pain with breathing. • Palpitations. • Syncope. 	Presence of ≥ 1 new or worsening of the following clinical symptoms:* 
 • Chest pain, pressure, or discomfort. • Dyspnea, shortness of breath, or pain with breathing. • Palpitations. • Syncope.
	OR , infants and children aged <12 years might instead have ≥ 2 of the following symptoms: 
 • Irritability. • Vomiting. • Poor feeding. • Tachypnea. • Lethargy. 	OR , infants and children aged <12 years might instead have ≥ 2 of the following symptoms: 
 • Irritability. • Vomiting. • Poor feeding. • Tachypnea. • Lethargy.
AND ≥ 1 new finding of 
 • Troponin level above upper limit of normal (any type of troponin). • Abnormal electrocardiogram (ECG or EKG) or rhythm monitoring findings consistent with myocarditis[§]. • Abnormal cardiac function or wall motion abnormalities on echocardiogram. • cMRI findings consistent with myocarditis[¶]. 	AND ≥ 1 new finding of 
 • Histopathologic confirmation of myocarditis[†]. • cMRI findings consistent with myocarditis in the presence of troponin level above upper limit of normal (any type of troponin). 	

Condition	Definition	
	AND 
 • No other identifiable cause of the symptoms and findings. 	AND 
 • No other identifiable cause of the symptoms and findings.
Acute pericarditis**	Presence of ≥ 2 new or worsening of the following clinical features: 
 • Acute chest pain^{††}. • Pericardial rub on exam. • New ST-elevation or PR-depression on EKG. • New or worsening pericardial effusion on echocardiogram or MRI. 	
Myopericarditis	This term may be used for patients who meet criteria for both myocarditis and pericarditis.	

Abbreviations: AV=atrioventricular; CDC=Centers for Disease Control and Prevention; CEAC=Cardiac Event Adjudication Committee; cMRI=cardiac magnetic resonance imaging; ECG or EKG=electrocardiogram; MRI=magnetic resonance imaging.

Note: An independent CEAC comprising medically qualified personnel, including cardiologists, will review suspected cases of myocarditis, pericarditis, and myopericarditis to determine if they meet Center for Disease Control and Prevention criteria for “probable” or “confirmed” events ([Gargano et al 2021](#)), and provide the assessment to the Sponsor. The CEAC members will be blinded to study treatment. Details regarding the CEAC composition, responsibilities, procedures, and frequency of data review will be defined in the CEAC charter.

* Persons who lack the listed symptoms but who meet other criteria may be classified as subclinical myocarditis (probable or confirmed).

[†] Using the Dallas criteria ([Aretz et al 1987](#)). Autopsy cases may be classified as confirmed clinical myocarditis on the basis of meeting histopathologic criteria if no other identifiable cause.

[§] To meet the ECG or rhythm monitoring criterion, a probable case must include at least one of 1) ST-segment or T wave abnormalities; 2) Paroxysmal or sustained atrial, supraventricular, or ventricular arrhythmias; or 3) AV nodal conduction delays or intraventricular conduction defects.

Using either the original or the revised Lake Louise criteria.

<https://www.sciencedirect.com/science/article/pii/S0735109718388430?via%3Dihubexternal> icon.

** <https://academic.oup.com/eurheartj/article/36/42/2921/2293375>external icon.

^{††} Typically described as pain made worse by lying down, deep inspiration, or cough, and relieved by sitting up or leaning forward, although other types of chest pain might occur.

Reference: ([Gargano et al 2021](#)).

**List of Abbreviations**

Abbreviation	Definition
AE	Adverse event
AESI	Adverse event of special interest
ANCOVA	Analysis of covariance
AR	Adverse reaction
BMI	Body mass index
CEAC	Cardiac Event Adjudication Committee
CI	Confidence interval
CSP	Clinical study protocol
CSR	Clinical study report
eCRF	Electronic case report form
eDiary	Electronic diary
EOS	End of study
FAS	Full analysis set
FDA	Food and Drug Administration
GLSM	Geometric least square means
GMFR	Geometric mean fold-rise
GMR	Geometric mean ratio
GMT	Geometric mean titer
HAI	Hemagglutination inhibition
IA	Interim analysis
ICF	Informed consent form
IST	Internal safety team
IVRS	Interactive Voice Response System
IWRS	Interactive Web Response System
LLOQ	Lower limit of quantification
MMRM	Mixed model repeated measures
MAAE	Medically attended adverse event
MedDRA	Medical Dictionary for Regulatory Activities
PT	Preferred term
RTPCR	Reverse Transcription Polymerase Chain Reaction
SAE	Serious adverse event
SAP	Statistical analysis plan
SAS	Statistical Analysis System
SD	Standard deviation
ULOQ	Upper limit of quantification

## 1. Introduction

This statistical analysis plan (SAP), which describes the planned analyses for Study mRNA-CRID-004, is based on the most recent approved clinical study protocol (CSP), dated 12-Apr-2023 and the electronic case report form (eCRF), dated 24-Aug-2023.

In addition to the information presented in the statistical analysis plan section of the protocol (Section 9) which provides the principal features of analyses for this study, this SAP provides statistical analysis details/data derivations. It also documents modifications or additions to the analysis plan that are not “principal” in nature and result from information that was not available at the time of protocol finalization.

Study mRNA-CRID-004 is a Phase 2, randomized, active-controlled, observer-blind, dose-ranging study to evaluate the safety, reactogenicity, and immunogenicity of mRNA vaccine candidate variations in healthy adults 18 to 49 years of age.

DuBu Research Biostatistics and programming team, designee of Moderna Biostatistics and Programming department, will perform the statistical analysis of the safety, reactogenicity, and immunogenicity data; Statistical Analysis System (SAS) Version 9.4 or higher will be used to generate all statistical outputs (tables, figures, listings, and datasets). The SAP will be finalized and approved prior to the first interim analysis (IA) clinical database lock and treatment unblinding for the study. If the methods in this SAP differ from the methods described in the protocol, the SAP will prevail.

## 2. Study Objectives

### 2.1. Primary Objective

The primary objective is the following:

- To evaluate the safety and reactogenicity of mRNA 1010 vaccine candidate variations.

### 2.2. Secondary Objectives

The secondary objective is the following:

- To evaluate the humoral immunogenicity of mRNA 1010 vaccine candidate variations at evaluable humoral immunogenicity timepoints.

### 2.3. Exploratory Objectives

CCI [REDACTED]

- CCI [REDACTED]  
[REDACTED]  
[REDACTED]

## 3. Study Endpoints

### 3.1. Primary Endpoints

The primary objective will be evaluated by the following endpoints:

- Solicited local and systemic adverse reactions (ARs) through 7 days after study intervention.
- Unsolicited adverse events (AEs) through 28 days after study intervention.
- Medically attended AEs (MAAEs) from Day 1 to end of study (EoS).
- Adverse events of special interest (AESIs) from Day 1 to EoS.
- Serious adverse events (SAEs) from Day 1 to EoS.
- AEs leading to study or treatment discontinuation from Day 1 to EoS.

### 3.2. Secondary Endpoint

The secondary objective will be evaluated by the following endpoints:

- Geometric mean titer (GMT) at indicated timepoints as measured by hemagglutination inhibition (HAI) assay.
- Geometric mean fold rise (GMFR), comparing each timepoint with D1 (Baseline) as measured by HAI assay.
- Percentage of participants with seroresponse for mRNA1010 at indicated timepoints, as measured by HAI assay.

### 3.3. Exploratory Endpoints

CCI [REDACTED]

[figure not shown]
[figure not shown]
- CCI
- 
- 

## 4. Study Design

### 4.1. Overall Study Design

This will be a randomized, observer-blind, Phase 2 study to evaluate the safety, reactogenicity and immunogenicity of mRNA-1010 vaccine candidate variations using a systems biology approach in healthy adults 18 to 49 years of age.

Three mRNA-1010 vaccine candidate versions will be evaluated:

- mRNA-1010: CCI
- 
- 
- 
- 
- 
- 
- 
- 
- 
- 
- 
- 
- 
- 
- 
- 
- 
- 
- 
- 
- 
- 
- 
- 
- 
- 
- 
- 
- 
- 
- 
- 
- 
- 
- 
- 
- 
- 
- 
- 
- 
- 
- 
- 
- 
- 
- 
- 
- 
- 
- 
- 
- 
- 
- 
- 
- 
- 
- 
- 
- 
- 
- 
- 
- 
- 
- 
- 
- 
- 
- 
- 
- 
- 
- 
- 
- 
- 
- 
- 
- 
- 
- 
- 
- 
- 
- 
- 
- 
- 
- 
- 
- 
- 
- 
- 
- 
- 
- 
- 
- 
- 
- 
- 
- 
- 
- 
- 
- 
- 
- 
- 
- 
- 
- 
- 
- 
- 
- 
- 
- 
- 
- 
- 
- 
- 
- 
- 
- 
- 
- 
- 
- 
- 
- 
- 
- 
- 
- 
- 
- 
- 
- 
- 
- 
- 
- 
- 
- 
- 
- 
- 
- 
- 
- 
- 
- 
- 
- 
- 
- 
- 
- 
- 
- 
- 
- 
- 
- 
- 
- 
- 
- 
- 
- 
- 
- 
- 
- 
- 
- 
- 
- 
- 
- 
- 
- 
- 
- 
- 
- 
- 
- 
- 
- 
- 
- 
- 
- 
- 
- 
- 
- 
- 
- 
- 
- 
- 
- 
- 
- 
- 
- 
- 
- 
- 
- 
- 
- 
- 
- 
- 
- 
- 
- 
- 
- 
- 
- 
- 
- 
- 
- 
- 
- 
- 
- 
- 
- 
- 
- 
- 
- 
- 
- 
- 
- 
- 
- 
- 
- 
- 
- 
- 
- 
- 
- 
- 
- 
- 
- 
- 
- 
- 
- 
- 
- 
- 
- 
- 
- 
- 
- 
- 
- 
- 
- 
- 
- 
- 
- 
- 
- 
- 
- 
- 
- 
- 
- 
- 
- 
- 
- 
- 
- 
- 
- 
- 
- 
- 
- 
- 
- 
- 
- 
- 
- 
- 
- 
- 
- 
- 
- 
- 
- 
- 
- 
- 
- 
- 
- 
- 
- 
- 
- 
- 
- 
- 
- 
- 
- 
- 
- 
- 
- 
- 
- 
- 
- 
- 
- 
- 
- 
- 
- 
- 
- 
- 
- 
- 
- 
- 
- 
- 
- 
- 
- 
- 
- 
- 
- 
- 
- 
- 
- 
- 
- 
- 
- 
- 
- 
- 
- 
- 
- 
- 
- [figure not shown] 150\%$  of the randomized vaccine product dose level will exclude a participant from the PP set based on the following rule ('Y' indicates exclusion):

**Table 2: PP Set Exclusion Criteria for Dosing Errors**

mRNA-1010

Actual Dose Received	Actual Dose Assigned	Randomized Dose
CCI		CCI
		Y
		Y

mRNA-1010.4

Actual Dose Received	Actual Dose Assigned	Randomized Dose	
CCI		CCI	
		Y	Y
			Y
		Y	
		Y	Y

mRNA-1010.6

Actual Dose Received	Actual Dose Assigned	Randomized Dose		
CCI		CCI		
		Y	Y	Y
			Y	Y
		Y		Y
		Y	Y	
		Y	Y	Y

The PPS will be used as the primary analysis set for analyses of immunogenicity unless otherwise specified. Participants will be analyzed according to the group to which they were randomized.

## 6. Statistical Analysis

### 6.1. General Considerations

The schedule of events is provided in [Appendix E](#).

**Continuous variables** will be summarized using the following descriptive summary statistics: the number of participants (n), mean, standard deviation (SD), median, minimum (min), and maximum (max).

**Categorical variables** will be summarized using counts and percentages.

**Baseline value**, unless specified otherwise, is defined as the most recent non-missing measurement (scheduled or unscheduled) collected before study vaccination.

For immunogenicity tests, the baseline is defined as the most recent non-missing measurement (scheduled or unscheduled) collected before or on the date of first dose of IP.

For the summary statistics of all numerical variables unless otherwise specified, the display precision will follow programming standards. Please see [Appendix A](#) for variable display standards.

When count data are presented, the percentage will be suppressed when the count is zero in order to draw attention to the non-zero counts. A row denoted “Missing” will be included in count tabulations where specified on the shells to account for dropouts and missing values. The denominator for all percentages will be the number of participants in that treatment group within the analysis set of interest, unless otherwise specified.

**Study day relative to injection** will be calculated as below:

- a) study day prior to injection will be calculated as: date of assessment/event – date of injection;
- b) study day on or after the date of injection will be calculated as: date of assessment/event – date of injection + 1.

**For calculation regarding antibody levels/concentrations**, antibody values reported as below lower limit of quantification (LLOQ) will be replaced by  $0.5 \times \text{LLOQ}$ . For values that are greater than the upper limit of quantification (ULOQ), if actual values are reported from the testing lab, the actual values will be used in analysis (not the assigned ULOQ value); if actual values are not reported by the testing lab and results are reported as ‘>ULOQ’, the assigned value of ULOQ will be used in analysis. Missing results will not be imputed.

The following **analysis periods for safety analyses** will be used in this study:

- Up to 7 days after vaccination injection: this period starts at the day of injection and continues through 6 subsequent days. This analysis period will be used for analyses of solicited ARs.
- Up to 28 days after vaccination injection: this period starts at the day of injection and continues through 27 subsequent days. This analysis period will be used as the primary analysis period for analyses of unsolicited AEs, unless specified otherwise.

- Throughout the study: this period starts at injection on Day 1 and continues through the earliest date of (study completion, discontinuation from the study, or death). This analysis period will be used for analyses of unsolicited AEs including any SAEs, MAAEs, AEs leading to discontinuation of study vaccine and/or study participation, and AESIs.

**Unscheduled visits:** Unscheduled visit measurements will be included in analysis as follows:

- In scheduled visit windows per specified visit windowing rules.
- In the derivation of baseline.
- In the derivation of maximum/minimum values and maximum/minimum change from baseline values for safety analyses.
- In individual participant data listings as appropriate.

**Visit windowing rules:** The analysis visit windows for protocol-defined visits are provided in [Appendix B](#).

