## 6.2. Background Characteristics

### 6.2.1. Participant Disposition

The number and percentage of participants in the following categories will be summarized by treatment group as defined in [Section 6.1](#) based on Randomization Set:

- Randomization Set
- Solicited Safety Set
- Safety Set
- Full Analysis Set
- Per-Protocol Set

The percentage will be based on participants in the Randomization Set.

The number of participants in the following categories will be summarized:

- Participants screened
- Screen failure participants
- Individual reasons for screen failure

The percentage of participants who screen failed will be based on the number of participants screened. The percentage of participants reporting each reason for screen failure will be based on the number of participants who screen failed.

The number and percentage of participants in each of the following disposition categories will be summarized overall and by treatment group based on the Randomization Set:

- Received study vaccine
- Completed study

- Prematurely discontinued the study and the reason for discontinuation

The number and percentage of participants will be summarized by site based on Randomization Set.

A participant disposition listing will be provided, including informed consent, participants who received study vaccine, participants who completed study, participants who discontinued from participation in the study, with reasons for discontinuation. A separate listing will be provided for screen failure participants with reasons for screen failure.

In addition, randomized participants with any inclusion and exclusion criteria violation will also be provided in a listing.

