### 6.4.2. Analysis of Humoral Immunogenicity Endpoints

Immunogenicity assessments of serum antibody levels as measured by HAI assay at CCI  
[REDACTED] will be included in the analyses below.

Data collected following intercurrent events ([Section 6.4.3](#)) will not be included in data summaries or inferential analyses described in this section.

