#### 6.4.2.1 Geometric Mean Titer and Geometric Mean Fold Rise

- The following immunogenicity endpoints will be evaluated: Geometric mean titer (GMT) at indicated timepoints as measured by HAI assay.
- Geometric mean fold rise (GMFR), comparing each timepoint with D1 (Baseline) as measured by HAI assay.

The GMT will be calculated using the following formula:

$$2^{\left\{ \frac{\sum_{i=1}^n \log_2(t_i)}{n} \right\}}$$

where  $t_1, t_2, \dots, t_n$  are  $n$  observed immunogenicity titers.

The GMFR measures the changes in immunogenicity titers within participants. The GMFR will be calculated using the following formula:

$$2^{\left\{ \frac{\sum_{i=1}^n \log_2(v_{ij}/v_{ik})}{n} \right\}} = 2^{\left\{ \frac{\sum_{i=1}^n \log_2(v_{ij}) - \log_2(v_{ik})}{n} \right\}}$$

where, for  $n$  participants,  $v_{ij}$  and  $v_{ik}$  are observed immunogenicity titers for participant  $i$  at time points  $j$  and  $k$ ,  $j \neq k$  and  $k$  is baseline. The 95% CIs for GMT and GMFR will be calculated based on the t distribution of the log-transformed values and then back transformed to the original scale for presentation.

- The following evaluations will be performed at baseline (Day 1) and each post-baseline time point: GMT of antibody levels with corresponding 95% CI will be provided at CCI [REDACTED]. GMTs with 95% CI will be plotted at each time point. The following descriptive statistics will also be provided at CCI [REDACTED] the number of participants (n), median, minimum, and maximum.
- GMFR of antibody levels with corresponding 95% CI will be provided at CCI [REDACTED] over pre-injection at (Day 1 [baseline]). GMFRs and corresponding 95% CI will be plotted at each post-baseline time point.

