### 6.4.2.3 Seroresponse

The immunogenicity endpoint of seroresponse is defined as the proportion of participants with an increase of antibody titers and concentrations from baseline below the LLOQ to  $\geq 4 \times$  LLOQ, or at least a 4-fold rise from baseline if baseline is  $\geq$  LLOQ.

- The number and percentage of participants with seroresponse from Day 1 (baseline) to CCI [REDACTED] will be provided with 2-sided 95% CI using the Clopper-

Pearson method. Seroresponse rate and corresponding 95% CI will be plotted at each post-baseline time point.

- CCI [REDACTED]
- [REDACTED]
- [REDACTED]
- [REDACTED]
- [REDACTED]
- [REDACTED]
- [REDACTED]

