#### **6.4.2.4 Proportion of participants with HAI titer $\geq 1:40$**

The number and percentage of participants with a HAI titer  $\geq 1:40$  at CCI [REDACTED] will be provided with 2-sided 95% CI using the Clopper-Pearson method.

CCI [REDACTED]

[REDACTED]

[REDACTED]

[REDACTED]

[REDACTED]

[REDACTED]

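### Does the SAP's default denominator for percentages undermine the seroresponse and HAI ≥1:40 rates?

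*SAP*

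**What the plan says.** SAP 6.1 sets a general rule for tables: "The denominator for all percentages will be the number of participants in that treatment group within the analysis set of interest, unless otherwise specified". The same section says of antibody values: "Missing results will not be imputed". It also provides for a row showing missing values, which "will be included in count tabulations where specified on the shells to account for dropouts and missing values".

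SAP 6.4.2, which governs all the humoral endpoints, adds that data collected after an intercurrent event "will not be included in data summaries or inferential analyses described in this section". SAP Table 3 (section 6.4.3) separates the consequences. Prohibited medication or a non-study influenza vaccine, and important visit-window deviations, remove the participant from the PPS. An intercurrent infection only censors the later titers.

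Within 6.4.2, the GMT formula in 6.4.2.1 runs over n "observed immunogenicity titers". The two binary summaries open with "The number and percentage of participants with seroresponse from Day 1 (baseline) to" (6.4.2.3) and "The number and percentage of participants with a HAI titer" (6.4.2.4). Each has a two-sided 95% Clopper-Pearson interval, and the readable text of neither names a denominator.

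Protocol Table 5 admits a participant to the PPS with a baseline and one or more post-injection assessments. Protocol 9.2 states that no formal hypothesis is tested.

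**The concern.** A participant can belong to the PPS and still have no usable titer at a particular visit, either because that sample was never taken or because the titer was censored after an infection. If the 6.1 default is applied mechanically, that participant adds one to the denominator and nothing to the numerator. The arithmetic is the same as imputing non-response, although the SAP says it does not impute, and censoring a titer would in effect score a failure.

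Three things would be affected. The reported rate would be biased downward. The exact interval would be computed with too large an n. The seroresponse rate at a visit would have a different n from the GMT and GMFR at that visit. If missing titers were unevenly spread over the six arms, the descriptive comparison between arms would shift as well.

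The SAP does write out a different denominator elsewhere. SAP 6.2.1 says: "The percentage of participants who screen failed will be based on the number of participants screened". The absence of such a sentence in the readable parts of 6.4.2.3 and 6.4.2.4 can therefore look like a decision to keep the default.

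**Working it through.** **1. Do the rules contradict each other?**

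- The 6.1 denominator rule is a default that gives way to anything specified elsewhere.
- The no-imputation sentence governs titer values. It does not mention denominators.
- The 6.4.2 sentence removes post-event data from the data summaries of that section, which include seroresponse and HAI ≥1:40. It does not remove the participant from the PPS.

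All three can be applied at once: full PPS N, no value filled in, censored titers dropped, and a missing row where the shells ask for one. So there is no contradiction. The open question is narrower: does the 6.4.2 exclusion, read with the no-imputation rule, count as specifying otherwise? A statistician can reasonably say yes, because a censored titer that still counts as a failure has not been kept out of the summary.

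The contrast with 6.2.1 carries little weight. People screened are not an analysis set, so the default could not apply to them and another denominator had to be written.

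**2. Who is affected?**

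- Late visits should still be completed (Protocol 7.3 and 8), and scheduled visits map to their nominal timepoint (SAP Appendix B).
- Important window deviations lead to PPS exclusion (SAP Table 3). A missed visit is a protocol deviation (Protocol 8) and can lead to exclusion if judged important for the immune response (SAP 6.2.6).
- Post-dose swabs are taken only at unscheduled visits, from symptomatic participants at the investigator's discretion (Protocol Table 1, footnote h). Infections can also be found by review of the AE page (SAP Table 3).

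What remains is a PPS member with a sample never taken at one visit, or with later titers censored for infection. The documents give no rate for either.

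**3. How large is the effect?**

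Inputs: arms of 60 and 30 (Protocol Table 4), which are upper bounds for the PPS. The plan states no figure for this point. Its only arm-size figures are AE-detection probabilities, and they reproduce with 1 − (1 − p)^n: 95.4% (n = 60, p = 5%), 83.9% (60, 3%), 95.0% (30, 9.5%) and 90.4% (30, 7.5%), against the stated 95%, 84%, 95% and 90%.

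Let x be responders, N the PPS participants in the arm and m those without a usable titer. Then:

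literal rate = x/N = [x/(N − m)] × (1 − m/N)

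The multiplier is 59/60 = 0.983 for 1 of 60, 57/60 = 0.950 for 3 of 60 and 29/30 = 0.967 for 1 of 30. Response rates near 50%, 70% and 90% are assumed. Intervals are exact Clopper-Pearson 95%.

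| N | m | Evaluable denominator | Literal default | Difference (points) |
|---|---|---|---|---|
| 60 | 1 | 30/59 = 50.8% (37.5–64.1) | 30/60 = 50.0% (36.8–63.2) | −0.8 |
| 60 | 1 | 41/59 = 69.5% (56.1–80.8) | 41/60 = 68.3% (55.0–79.7) | −1.2 |
| 60 | 1 | 53/59 = 89.8% (79.2–96.2) | 53/60 = 88.3% (77.4–95.2) | −1.5 |
| 60 | 3 | 28/57 = 49.1% (35.6–62.7) | 28/60 = 46.7% (33.7–60.0) | −2.5 |
| 60 | 3 | 40/57 = 70.2% (56.6–81.6) | 40/60 = 66.7% (53.3–78.3) | −3.5 |
| 60 | 3 | 51/57 = 89.5% (78.5–96.0) | 51/60 = 85.0% (73.4–92.9) | −4.5 |
| 30 | 1 | 14/29 = 48.3% (29.4–67.5) | 14/30 = 46.7% (28.3–65.7) | −1.6 |
| 30 | 1 | 20/29 = 69.0% (49.2–84.7) | 20/30 = 66.7% (47.2–82.7) | −2.3 |
| 30 | 1 | 26/29 = 89.7% (72.6–97.8) | 26/30 = 86.7% (69.3–96.2) | −3.0 |

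With m = 0 the two columns agree. The evaluable intervals are 17.0 points (96.2 − 79.2) to 38.1 points (67.5 − 29.4) wide, and every literal interval contains the matching evaluable estimate.

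**The case for a change.** The best case for a change is reproducibility. Two programmers could each defend a different number for a named secondary endpoint. One would follow 6.1 to the letter, and the other would hold that 6.4.2 overrides it. The literal result is numerically the same as imputing non-response, and the shift is always downward. Protocol 9.5 also promises that the SAP will describe how missing data are handled, and a sentence naming the denominator would cost almost nothing. With more missing titers the gap grows: at 10% not evaluable it is about 5 to 9 points (for example 38/54 = 70.4% against 38/60 = 63.3%).

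Some of this stands. The readable text does leave the choice open, and the literal reading would be the poorer one. But the SAP does address missing titers, through no imputation, censoring, and missing rows where the shells call for them. The 10% scenario assumes 6 of 60 per-protocol participants without a usable titer at one visit. Nothing in the documents supports that rate, though nothing excludes it. The case also depends on text that cannot be read: the rest of 6.4.2.3 and 6.4.2.4 is blacked out, the SAP's own PPS definition is unreadable and the shells are not available. A denominator that may be stated there cannot be called absent from the plan.

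**Conclusion.** No change is needed. This is a gap of detail that an analyst fills sensibly: 6.4.2 keeps post-event data out of its summaries and missing titers are not imputed, so the natural denominator is the PPS participants with a usable titer at the visit, the same n as for the GMT. The baseline needed for the fold rise is already a PPS entry condition in Protocol Table 5. Naming that denominator and printing the evaluable n in the tables would be harmless good practice, but the plan does not fail without it.

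If the default were taken literally, the understatement would be nil with complete data, 0.8 to 3.0 points with one participant missing in an arm, and 2.5 to 4.5 points with three of 60 missing. These sizes rest on assumed response rates of 50% to 90%, assumed missing counts and a PPS equal to the randomized arm. The estimates are descriptive and no hypothesis is tested, so no formal decision depends on the choice.
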